#### **7.1.7. Analysis Related to HIV RNA**

Proportion of subjects with HIV virologic rebound during the study will be summarized by treatment group for subjects who are on ARV treatment at enrollment.

Subjects with HIV virologic rebound is defined as meeting all three following criteria:

- at least two HIV RNA  $\geq 50$  copies/mL at 2 consecutive post-baseline visits which are at least 2 weeks apart based on actual dates;
- on ARV at baseline;
- HIV RNA  $< 50$  copies/mL at baseline.

Listing of subjects with HIV virologic rebound will be presented together with their information on HIV RNA, CD4 counts (absolute and %), HCV RNA, current ARV regimen, HIV and HCV history and HCV treatment during the study.

HIV RNA, change and percentage change from baseline in HIV RNA for subjects not on ARV at baseline will be listed by visit for each treatment group.

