## 2. OBJECTIVES

The primary objectives of this study are:

- To determine the efficacy of treatment with GS-7977 + RBV as measured by the proportion of subjects with sustained viral response 12 weeks after discontinuation of therapy (SVR12)
- To evaluate the safety and tolerability of GS-7977 + RBV as assessed by review of the accumulated safety data, including HIV-RNA and CD4 T-cell percent

The secondary objectives of this study are as follows:

- To determine the proportion of subjects who attain SVR at 4 and 24 weeks after discontinuation of therapy (SVR4 and SVR24)
- To evaluate the kinetics of circulating HCV RNA during treatment and after treatment discontinuation
- To evaluate the emergence of viral resistance to GS-7977 during treatment and after treatment discontinuation

The exploratory objectives of this study are:

- To identify or validate genetic markers that may predict the natural history of disease, response to therapy and/or the tolerability of medical therapies through genetic discovery research (e.g., pharmacogenomics), in subjects who provide their separate and specific consent
- To assess the effect of treatment on health related quality of life

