For the analyses of continuous HCV RNA efficacy data, any subject with a missing value in a visit window that is bracketed by prior and subsequent values of “< LLOQ TND” will be set to “< LLOQ TND” (ie, 24 IU/mL). Subjects with a missing data point preceded and followed by values that are “< LLOQ detected”, preceded by “< LLOQ detected” and followed by “< LLOQ TND”, or preceded by “< LLOQ TND” and followed by “< LLOQ detected” will be set to “< LLOQ detected” (ie, 24 IU/mL). No other imputation will be performed for continuous data.

Missing cirrhosis will be imputed as no cirrhosis.

Except for the imputation rules described above, values for other missing data (including all safety data) will not be imputed.

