## 6. EFFICACY ANALYSES

### 6.1. Definition of the Efficacy Endpoints

The efficacy endpoints for this safety update include the following:

- SVR12 defined as HCV RNA < LLOQ (ie, < 25 IU/mL) at 12 weeks after study drug cessation for the full analysis set. The Roche COBAS® Taqman® HCV Test v2.0 for use with the High Pure System will be used to measure HCV RNA.
- Sustained virologic response 4 weeks after stopping all study drugs (SVR4) defined as HCV RNA < LLOQ (ie, < 25 IU/mL) at 4 weeks after study drug cessation for the full analysis set
- The proportion of subjects with HCV RNA below LLOQ (ie, < 25 IU/mL) while on treatment by study visit
- The proportion of subjects with on-treatment and posttreatment virologic failure, defined as the following:
  - On-treatment virologic failures
    - HCV RNA  $\geq$  25 IU/mL after having previously had HCV RNA < 25 IU/mL while on treatment, confirmed with 2 consecutive values (Note: second confirmation value can be posttreatment) or last available on-treatment measurement with no subsequent follow-up values (ie, breakthrough)
    - $>1 \log_{10}$  IU/mL increase in HCV RNA from nadir while on treatment, confirmed with 2 consecutive values (Note: second confirmation value can be posttreatment) or last available on-treatment measurement with no subsequent follow up values (ie, rebound)
    - HCV RNA persistently  $\geq$  25 IU/mL through 8 weeks of treatment (ie, nonresponse)
  - Relapse
    - HCV RNA  $\geq$  25 IU/mL during the posttreatment period having achieved HCV RNA < 25 IU/mL at end of treatment, confirmed with 2 consecutive values or last available posttreatment measurement

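### The HIV rebound summary (SAP 7.1.7, Table 21) has no rule for a last HIV RNA value at or above 50 copies/mL that is never confirmed, so it can understate possible rebound

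*Combined protocol and SAP*

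**What the plan says.** SAP 7.1.7 sets the summary: "Proportion of subjects with HIV virologic rebound during the study will be summarized by treatment group for subjects who are on ARV treatment at enrollment". Its definition is conjunctive: "Subjects with HIV virologic rebound is defined as meeting all three following criteria". The criteria are ARV use at baseline, HIV RNA below 50 copies/mL at baseline, and values of at least 50 "copies/mL at 2 consecutive post-baseline visits which are at least 2 weeks apart based on actual dates".

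SAP 3.6.1 gives imputation rules for HCV RNA and cirrhosis status, then states that "values for other missing data (including all safety data) will not be imputed". HIV RNA is handled as safety laboratory data (SAP 3.7.2), so no missing-data rule reaches it.

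Protocol 3.4 also requires two consecutive values at least two weeks apart, and it asks a subject with an unconfirmed rebound to return for a confirmatory draw. It does not say how to classify a subject who does not return. Protocol 3.6 asks for the confirmation as soon as possible and no later than 2 weeks after the initial observation is determined.

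For HCV, SAP 6.1 does deal with a missing second value. On-treatment breakthrough may rest on two consecutive values "or last available on-treatment measurement with no subsequent follow-up values (ie, breakthrough"; rebound has the same alternative. Relapse is "confirmed with 2 consecutive values or last available posttreatment measurement".

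**The concern.** A subject suppressed at baseline whose first raised HIV RNA is also the last one on file cannot meet the two-visit criterion. The subject stays in the denominator and adds nothing to the numerator, exactly like a subject who was suppressed throughout. Table 21 does not separate the two.

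This can happen in four ways: the raised value comes at the last scheduled visit and no retest is obtained; the subject drops out after it; the database is cut after it; or the only retest is too early to count. The cut matters because this SAP governs an analysis triggered when Groups 1 and 3 reach post-treatment Week 12 (SAP 2.1), with ongoing subjects analysed on whatever is in the snapshot (SAP 7.2).

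The HIV effect of the regimen is a stated interest. Protocol Section 2 words the safety objective "as assessed by review of the accumulated safety data, including HIV-RNA and CD4 T-cell percent". Table 21 is the only table of HIV RNA results, so an incomplete numerator there is not corrected by another summary.

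**Working it through.** The documents state no expected HIV rebound rate and no number of unconfirmed values, so there is no plan figure to reproduce.

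**1. The rule applied to example subjects.** Days are from first dose in the 12-week group, so post-treatment Week 24 is day 84 + 168 = 252. HIV RNA levels are invented for illustration.

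- Below 50 through day 168, first value at or above 50 on day 252, nothing later: no rebound.
- First value at or above 50 at Week 6 (day 42), then dropout: no rebound.
- Raised on day 252, raised again at a retest on day 262 (262 − 252 = 10 days): no rebound.
- Raised on day 252, raised again on day 266 (14 days): rebound.
- 80 copies/mL on day 42, then 20 on day 56: no rebound.

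A clause that flags a last available value at or above 50 would pick up the first three. It leaves the fourth as confirmed and does not flag the fifth.

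**2. Where the first three subjects appear.** Listing 22.1 and Table 21 show only subjects who meet the definition. HIV RNA is not among the analytes in SAP 7.2.1 and has no grade in protocol Appendix 3. Listing 22.2 covers only subjects not on ARV. That leaves Listing 20.

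**3. Retest timing.** The SAP needs at least 14 days between draws. Protocol 3.6 allows at most 14 days from determination of the first result. If the result takes r days, both are met only from day 14 to day 14 + r after the first draw. A retest done as soon as possible can fall before that interval, and then counts only if a further value at or above 50 follows at least 14 days after it.

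**4. Possible size.** Appendix 2 schedules HIV RNA at Weeks 1, 2, 4, 6, 8, 10 and 12 (also 16, 20 and 24 in the 24-week groups) and at post-treatment Weeks 4, 12 and 24. Assume persistent rebound, onset uniform over scheduled follow-up, and no retest. The share first seen at the last visit is the last interval divided by total follow-up:

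| Last visit | 12-week group | 24-week groups |
|---|---|---|
| Post-treatment Week 24 | 12/36 = 33% | 12/48 = 25% |
| Post-treatment Week 12 | 8/24 = 33% | 8/36 = 22% |
| Post-treatment Week 4 | 4/16 = 25% | 4/28 = 14% |

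The Week 12 row matters for subjects cut off by the snapshot. The Week 4 row applies to subjects with HCV RNA at or above LLOQ at that visit, who have no later scheduled visits (protocol 3.2).

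Now assume instead that all onset is on treatment and the subject attends the end-of-treatment and post-treatment Week 4 visits. The first raised value comes no later than end of treatment, and a value about 4 weeks later exists, so the share is about 0%. The range is therefore about 0% to 33% before any retest.

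**5. Effect of one subject.** Up to 10% of subjects may be ARV-untreated. Taking 90% as treated gives 0.9 × 55 ≈ 50 and 0.9 × 115 ≈ 104. One unconfirmed subject then moves the proportion by 1/50 = 2.0 or 1/104 = 1.0 percentage points. With one confirmed and one unconfirmed subject in the smaller group, the table would show 2.0% confirmed and 4.0% in total.

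**The case against.** The strongest reply is that the SAP does what protocol 3.4 says. The protocol defines rebound by two values and calls the first one unconfirmed, and the notes to its Figure 3-1 keep the subject on the current ARV regimen if it is not confirmed. A single value at or above 50 may be transient. This stands: requiring confirmation is sound, and a reader who takes every unconfirmed last value as lost HIV control goes beyond the documents. Counting single values as rebounds would err in the other direction.

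The retest in protocol 3.4 also closes part of the gap. It may be unscheduled, and the SAP measures spacing on actual dates, so the absence of a scheduled visit after post-treatment Week 24 is not decisive. What remains is subjects who do not return, who drop out, who are at the data cut, or who are retested too early.

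The HCV contrast can be defended. HCV failure is an efficacy endpoint in which missing data count against the drug, while safety data are not imputed. The two conventions need not match, so the contrast is not an error in itself. It does show that the SAP recognised the missing-second-value problem and has a workable form of words for it.

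Finally, the stakes are limited. HIV RNA is named in the objective only in protocol Section 2, not in the synopsis, protocol 9.1.1 or SAP 1.1.1. The primary safety endpoint is an AE leading to permanent discontinuation. Table 21 is descriptive, Listing 20 keeps every value, and neither subject management nor the DSMB trigger in protocol 3.4 is tied to that table. All of this stands. It limits the weight of the point without supplying the missing rule.

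**Conclusion.** The gap is real and narrow. No passage classifies a last HIV RNA value that is the first at or above 50, or a raised pair less than 14 days apart. These subjects are counted as non-events in Table 21 and are left out of Listing 22.1, so the table can understate possible rebound.

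The size is unknown. The range of about 0% to 33% is the share of persistent rebounds first seen at the last scheduled visit before any retest. It depends on the assumed onset pattern, not on any figure in the documents. A reader might go further and estimate a percentage of true rebounds missed, by weighting the shares with the assumed SVR12 rates and guessing a return rate for retests. The documents give neither an onset pattern nor a return rate, SVR12 is only a rough proxy for length of HIV follow-up, and full follow-up to post-treatment Week 24 does not describe the data cut in SAP 2.1. No such estimate is supported.

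**What to change.** In SAP 7.1.7 and Table 21, keep the confirmed-rebound row as it is. Add, by treatment group:

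- a row labelled as unconfirmed: subjects on ARV with baseline HIV RNA below 50 copies/mL whose last available HIV RNA is at or above 50 and who do not meet the confirmed definition;
- a row giving the total of confirmed and unconfirmed subjects over the same denominator.

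Include the unconfirmed subjects in Listing 22.1, flagged as such and with the HIV RNA level shown, so that a low value and a high one can be told apart.

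Reconcile the confirmation timing in protocol 3.6 with the minimum spacing in protocol 3.4 and SAP 7.1.7. Which timing should apply is for the sponsor to decide.

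The added rows and the wider listing use data already collected and leave the confirmed definition untouched. The downside is that some unconfirmed values will be transient, which is why they need their own label.

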Study visits will occur at Screening, Baseline (Day 1) and at the end of Weeks 1, 2, 4, 6, 8, 10, and 12 for the Genotype 2 and 3 HCV treatment naïve subjects. Additional study visits occur at the end of Weeks 16, 20 and 24 for Genotype 1 HCV treatment naïve and HCV treatment-experienced Genotypes 2 and 3. Post-treatment follow-up visits will be performed for all subjects at 4 weeks following the last dose of study drug. Subjects with HCV RNA < lower limit of quantification (LLOQ) at post-treatment Week 4 will return at post-treatment Week 12 and Week 24.

Screening assessments include physical examination, vital signs, concomitant medications, safety laboratory tests, HCV RNA, HIV-1 RNA, CD4 T-cell count and percent, serology (HIV, HCV, HBV), hemoglobin A1c (HbA1c), Fibrotest®/APRI, imaging for HCC (cirrhotics only), lipase, serum  $\beta$ -hCG (females of child bearing potential only), thyroid stimulating hormone (TSH), IL28B genotyping, urinalysis and urine drug screen.

On-treatment assessments include adverse events (AEs), concomitant medications, physical examination, vital signs, safety laboratory tests, HCV RNA, HIV-1 RNA, CD4 T-cell count and percent, pharmacokinetic samples, and urine pregnancy tests (females of child bearing potential only).

Post-treatment assessments include AEs, concomitant medications, vital signs, safety laboratory tests, HCV RNA, HIV-1 RNA, CD4 T-cell count and percent, and urine pregnancy tests (females of child bearing potential only).

Quality of life surveys will be performed at Baseline/Day 1, Week 4, Week 12, Week 24 (as appropriate for the treatment regimen), Early Termination, post-treatment Week 4, and post-treatment Week 12 and post-treatment Week 24 to assess quality of life.

Samples will be collected at Baseline and every visit thereafter for viral sequencing.

For subjects who provide their additional and specific consent, an appropriate blood sample will be collected at the Baseline visit for human pharmacogenomic testing (this sample may be drawn after Baseline, if necessary).

---

---

**Test Product, Dose, and Mode of Administration:** GS-7977 will be administered orally using a tablet strength of 400 mg. RBV will be administered orally using a tablet strength of 200 mg.

Subjects will take 1000-1200 mg RBV every day in a divided daily dose (1000 mg for subjects weighing < 75 kg and 1200 mg for subjects weighing ≥ 75 kg).

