### **3.4. HIV Virologic Rebound Criteria**

Subjects who meet the criteria listed below will be considered to have HIV virologic rebound:

- At any visit, have at least two consecutive plasma HIV-1 RNA levels  $\geq$  50 copies/mL (at least two weeks apart)

Following the unconfirmed HIV virologic rebound, subjects will be asked to return to the clinic for a scheduled or unscheduled blood draw for confirmation of HIV virologic rebound. If HIV virologic rebound is confirmed at the scheduled or unscheduled visit, the blood samples from this visit will be used for HIV-1 genotype/phenotype testing if the HIV-1 RNA is  $\geq$  400 copies/mL. Plasma samples with  $<$  400 copies/mL of HIV-1 RNA will not be analyzed as the protease/reverse transcriptase genotype/phenotype assays used in this study are not validated when plasma HIV-1 RNA levels are  $<$  400 copies/mL.

[figure not shown]
If greater than 20% of subjects enrolled on any specific ARV regimen experience virologic breakthrough, an ad-hoc DSMB meeting will be convened to evaluate the safety of continuing enrollment of subjects on this specific ARV therapy.

HCV medications should be continued unless safety events warrant the discontinuation of these medications, as outlined in Section 3.7 of the protocol.

These criteria only apply to subjects currently on ARV treatment and have HIV-1 RNA levels  $<$  50 copies/mL. These do not apply to subjects meeting the ARV untreated parameters outlined in the Inclusion criteria of the protocol.

Please refer to [Figure 3-1](#) for the management of subjects who meet the criteria for HIV virologic rebound.

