### **3.6. HIV Resistance Monitoring**

Plasma samples for HIV resistance testing will be collected from subjects who experienced HIV virologic rebound. Following the unconfirmed HIV virologic rebound, confirmation should be performed as soon as possible but within 2 weeks after determination of initial observation. If HIV rebound is confirmed, the samples will be used for HIV-1 genotype/phenotype testing.

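### The 14-day spacing rule for HIV virologic rebound can leave some short rebounds in the first 12 weeks out of SAP Table 21

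*Combined protocol and SAP*

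**What the plan says.** Protocol 3.4 defines HIV virologic rebound as at least two consecutive HIV-1 RNA values at or above 50 copies/mL that are "at least two weeks apart". It applies this to subjects who are on ARV with HIV RNA below 50. After a first raised value, "subjects will be asked to return to the clinic for a scheduled or unscheduled blood draw for confirmation of HIV virologic rebound".

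Protocol 3.6 sets the timing of that draw: "confirmation should be performed as soon as possible but within 2 weeks after determination of initial observation".

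SAP 7.1.7 keeps the protocol's minimum spacing and makes it operational: the two raised values must occur at "2 consecutive post-baseline visits which are at least 2 weeks apart based on actual dates", in a subject on ARV at baseline with baseline HIV RNA below 50. It then states that the proportion with "HIV virologic rebound during the study will be summarized by treatment group", among subjects on ARV at enrollment. This becomes Table 21 and Listing 22.1.

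The protocol synopsis places on-treatment visits "at the end of Weeks 1, 2, 4, 6, 8, 10, and 12 for the Genotype 2 and 3 HCV treatment naïve subjects", with Weeks 16, 20 and 24 added for the 24-week groups. Protocol 6.2.2 to 6.2.4 and 6.3 give every visit a tolerance of 3 days either way. HIV RNA is measured at every visit, through post-treatment Week 24.

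**The concern.** A minimum spacing of 14 actual days is being applied to visits whose target spacing is exactly 14 days. Any pair in which the second visit is early relative to the first fails the rule, although both visits are within tolerance and both values are raised. Separately, a site that confirms promptly, as protocol 3.6 asks, can produce a second raised value that is too close to the first to count. SAP 7.1.7 does not say how an unscheduled confirmation draw enters a rule written in terms of consecutive visits.

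Protocol Section 2 names HIV RNA within the primary safety objective. Table 21 is the only planned table of HIV RNA control in ARV-treated subjects: the numeric laboratory summaries in SAP 7.2.1 cover CD4 but not HIV RNA, and the grading scale in protocol Appendix 3 has no HIV RNA grade. A spacing rule of this kind can only remove cases, so the error makes the regimen look safer for HIV control. Short runs are plausible, because the notes to protocol Figure 3-1 allow a new ARV regimen after confirmed rebound.

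**Working it through.** The documents state no expected rebound rate, so there is no figure of the plan's own to reproduce. The check is whether visits made on schedule can meet the rule.

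**Gaps between scheduled visits.** Let a and b be the offsets, in whole days from −3 to +3, of the first and second visit. Actual gap = nominal gap + b − a, so it ranges over nominal ± 6. There are 7 × 7 = 49 offset pairs.

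| Adjacent visits | Nominal gap (days) | Actual range (days) | Offset pairs under 14 days |
|---|---|---|---|
| Week 1–2 | 7 | 1–13 | 49/49 |
| Weeks 2–4, 4–6, 6–8, 8–10, 10–12 | 14 | 8–20 | 21/49 |
| Later on-treatment gaps; end of treatment to post-treatment Week 4 | 28 | 22–34 | 0/49 |
| Post-treatment Week 4–12 | 56 | 50–62 | 0/49 |
| Post-treatment Week 12–24 | 84 | 78–90 | 0/49 |

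**Share of 14-day pairs lost.** The gap is under 14 when b < a. For independent offsets with the same weights w, P(b < a) = (1 − Σw²)/2. The documents do not give the scatter of visits, so three assumptions are shown:

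- Uniform: Σw² = 7 × (1/7)² = 1/7, giving 3/7 = 42.9%.
- Triangular (weights 1, 2, 3, 4, 3, 2, 1 over 16): Σw² = 44/256, giving 41.4%.
- 60% of visits exactly on the day (0.12, 0.05 and 0.03 at 1, 2 and 3 days on each side): Σw² = 0.3956, giving 30.2%.

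**Rebound lasting over k fortnightly visits.** It is missed only if every adjacent gap is under 14 days, that is, if the offsets strictly decrease. With uniform offsets the chance is C(7,k)/7^k: 21/49 = 42.9% for k = 2, 35/343 = 10.2% for k = 3, and 35/2401 = 1.5% for k = 4.

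**Prompt confirmation.** The protocol 3.6 limit runs from determination of the first result, not from the sample date. If laboratory turnaround is L days (not in the documents) and the draw is c = 1 to 14 days later, the gap from the first sample is L + c. It is under 14 for 13 − L of the 14 possible days: 13/14 at L = 0, 11/14 at L = 2, 8/14 at L = 5, and 6/14 at L = 7. These count possible days and are not probabilities; asking for confirmation as soon as possible favours the earlier ones.

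**Unscheduled draws.** Take values at or above 50 on Days 29, 36 (unscheduled) and 43.

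- If every draw is a visit, the gaps are 7 and 7 days and no rebound is counted.
- If the windows of SAP 3.7.2 and the selection rule of SAP 3.7.3 apply, Day 29 is Week 4 (Days 22–35). Days 36 and 43 both fall in Week 6 (Days 36–49, nominal Day 42), and Day 43 is chosen as closer (1 day against 6). Days 29 and 43 are 14 days apart, so the subject counts.
- The window reading has its own loss. With draws on Days 29 and 34, both are in Week 4 and Day 29 is chosen (1 day from Day 28 against 6), so the confirmation drops out.

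**The case against.** The strongest reply is that the SAP simply follows protocol 3.4. That is correct: the two-week minimum is the protocol's, and the underlying conflict is between protocol 3.4 and 3.6. The SAP adds only visits and actual dates, and leaves unscheduled draws undefined.

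A reader might infer that confirmed rebounds as a class go uncounted. The documents do not support that. Even with uniform offsets, 28/49 = 57% of 14-day pairs qualify, and every scheduled gap of 28 days or more qualifies unless an unscheduled draw intervenes. A confirmation within the protocol 3.6 limit can also fall 14 or more days after the first sample. Nor is an unscheduled draw certain to break a qualifying pair; under the SAP's window rules the Day 29/36/43 subject is counted.

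A reader might also infer that the protocol's safety trigger is disabled, because it acts by ARV regimen while Table 21 is by treatment group. The trigger reads "If greater than 20% of subjects enrolled on any specific ARV regimen experience virologic breakthrough". It convenes an ad-hoc DSMB meeting about continued enrollment, and it uses a different term from the defined rebound. This SAP serves the EMEA response and AASLD analysis, and nothing says that Table 21 feeds the trigger.

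It is also fair to say that the raw data remain visible: Listing 20 gives HIV RNA for the whole safety set. The primary safety endpoint is AEs leading to permanent discontinuation, and the laboratory summaries carry no inference. These points limit the consequence. They do not make the Table 21 proportion right, and Listing 22.1 depends on the same rule.

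**Conclusion.** The concern holds in a limited form. Some short rebounds in the first 12 weeks can be missed. For a rebound seen at exactly two adjacent fortnightly visits between Weeks 2 and 12, the chance of loss is about 30% to 43%, assuming independent offsets within the 3-day tolerance. A rebound seen only at Weeks 1 and 2 is always lost. Some promptly confirmed rebounds may also be lost, in a number that depends on laboratory turnaround and on how unscheduled draws are treated, neither of which is stated. Rebound lasting over three or four fortnightly visits is missed about 10% or 1.5% of the time.

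The 43% should not be read as the undercount in Table 21. It is conditional on a two-visit rebound in that period and on uniform offsets, and the documents give no rate for such rebounds.

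The denominator is also wider than the numerator: it includes everyone on ARV at enrollment, whereas a case needs baseline HIV RNA below 50. This too pulls the proportion down, but only slightly, because inclusion criterion 9 already requires screening HIV RNA below 50 in ARV-treated subjects.

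This should be fixed; it does not call the study's conclusions into question.

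**What to change.** In SAP 7.1.7 and Table 21:

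1. Keep the protocol 3.4 definition, but measure the 14 days from the first to the last value of an unbroken run at or above 50 copies/mL, using scheduled and unscheduled draws. Three fortnightly visits then span at least 28 − 6 = 22 days, Weeks 1, 2 and 4 span at least 21 − 6 = 15 days, and Days 29/36/43 span 14, so all of these count.
2. Beside it, report any two consecutive values at or above 50 regardless of interval. This is needed because a run of only two values 8 to 13 days apart still fails the first row. Lowering the 14-day minimum instead would depart from protocol 3.4 and need an arbitrary threshold.
3. List subjects whose last value is at or above 50 and unconfirmed.
4. Restrict the denominator to subjects on ARV with baseline HIV RNA below 50, which also matches the scope stated in protocol 3.4.
5. Rows by ARV regimen at enrollment are optional.

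Protocol 3.4 and 3.6 must be reconciled on the timing of confirmation. Which timing to adopt is for the sponsor.

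The cost is one extra derivation, a few table rows, a short listing and a protocol clarification. The supplementary row will include some transient blips, so it should be labelled as such and read beside the main row.
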